**Table 16-2 Follow Up Requirements for Liver Events and Laboratory Triggers**

Criteria	Actions required	Follow-up monitoring
Potential Hy's Law case a	
 
Discontinue the study treatment immediately
 
Hospitalize, if clinically appropriate
 
Establish causality
 
Complete liver CRF
 
	ALT, AST, TBL, Alb, PT/INR, ALP and $\gamma$ -GT until resolution c (frequency at investigator discretion)
ALT or AST		
for patients with normal baseline: $> 8 \times$ ULN For patients with elevated baseline $> 8 \times$ ULN or $> 500$ U/L whichever comes first	
 
Discontinue the study treatment immediately
 
Hospitalize if clinically appropriate
 
Establish causality
 
Complete liver CRF
 
	ALT, AST, TBL, Alb, PT/INR, ALP and $\gamma$ GT until resolution c (frequency at investigator discretion)
For patients with normal baseline: $> 5$ to $\leq 8 \times$ ULN For patients with elevated baseline: $>5$ to $\leq 8 \times$ ULN or $>5X$ ULN to $\leq 500$ U/L whichever comes first	
 
Repeat LFT within 48 hours
 
If elevation persists, continue follow-up monitoring
 
If elevation persists for more than 2 weeks, discontinue the study drug
 
Establish causality
 
Complete liver CRF
 
	ALT, AST, TBL, Alb, PT/INR, ALP and $\gamma$ GT until resolution c (frequency at investigator discretion)
$> 3 \times$ ULN accompanied by symptoms b	
 
Discontinue the study treatment immediately
 
Hospitalize if clinically appropriate
 
Establish causality
 
Complete liver CRF
 
	ALT, AST, TBL, Alb, PT/INR, ALP and $\gamma$ GT until resolution c (frequency at investigator discretion)
$> 3$ to $\leq 5 \times$ ULN (patient is asymptomatic)	
 
Repeat LFT within the next week
 
If elevation is confirmed, initiate close observation of the patient
 
	Investigator discretion Monitor LFT within 1 to 4 weeks
ALP (isolated)		
$> 2 \times$ ULN (in the absence of known bone pathology)	
 
Repeat LFT within 48 hours
 
If elevation persists, establish causality
 
Complete liver CRF
 
	Investigator discretion Monitor LFT within 1 to 4 weeks or at next visit
TBL (isolated)		

Criteria	Actions required	Follow-up monitoring
> 2 × ULN (in the absence of known Gilbert syndrome)	
 
Repeat LFT within 48 hours
 
If elevation persists, discontinue the study drug immediately
 
Hospitalize if clinically appropriate
 
Establish causality
 
Complete liver CRF
 
	ALT, AST, TBL, Alb, PT/INR, ALP and γGT until resolution c (frequency at investigator discretion) Test for hemolysis (e.g., reticulocytes, haptoglobin, unconjugated [indirect] bilirubin)
> 1.5 to ≤ 2 × ULN (patient is asymptomatic)	
 
Repeat LFT within the next week
 
If elevation is confirmed, initiate close observation of the patient
 
	Investigator discretion Monitor LFT within 1 to 4 weeks or at next visit
Jaundice	
 
Discontinue the study treatment immediately
 
Hospitalize the patient
 
Establish causality
 
Complete liver CRF
 
	ALT, AST, TBL, Alb, PT/INR, ALP and γGT until resolution c (frequency at investigator discretion)
Any AE potentially indicative of a liver toxicity*	
 
Consider study treatment interruption or discontinuation
 
Hospitalization if clinically appropriate
 
Establish causality
 
Complete liver CRF
 
	Investigator discretion

aElevated ALT/AST > 3 × ULN and TBL > 2 × ULN but without notable increase in ALP to > 2 × ULN

b(General) malaise, fatigue, abdominal pain, nausea, or vomiting, or rash with eosinophilia

cResolution is defined as an outcome of one of the following: (1) return to baseline values, (2) stable values at three subsequent monitoring visits at least 2 weeks apart, (3) remain at elevated level after a maximum of 6 months, (4) liver transplantation, and (5) death.

[Chalasani and Regev 2016](#)

### 16.3 Appendix 3: Specific Renal Alert Criteria and Actions and Event Follow-up

**Table 16-3 Specific Renal Alert Criteria and Actions**

Serum Event	
Serum creatinine increase 25 – 49% compared to baseline	Confirm 25% increase after 24-48h Follow up within 2-5 days
Acute Kidney Injury: Serum creatinine increase 50% compared to baseline	Follow up within 24-48h if possible Consider study treatment interruption Consider patient hospitalization /specialized treatment
Urine Event	
Albumin-creatinine ratio increase $\geq 2$ fold from baseline value	Confirm value after 24-48h Perform urine microscopy Consider study treatment interruption / or discontinuation
	Blood glucose (fasting) Perform serum creatinine, UACR
New dipstick hematuria $\geq 1+$ not due to trauma	Urine sediment microscopy Perform serum creatinine, UACR
For all renal events:	
Document contributing factors in the CRF: co-medication, other co-morbid conditions, and additional diagnostic procedures performed	
Monitor patient regularly (frequency at investigator's discretion) until either:	
Event resolution: sCr within 10% of baseline or albumin-creatinine ratio within 50% of baseline, or	
Event stabilization: sCr level with $\pm 10\%$ variability over last 6 months or albumin-creatinine ratio stabilization at a new level with $\pm 50\%$ variability over last 6 months.	

[Bakris et al 2015](#), [de Zeeuw et al 2014](#)

**Document History – Changes compared to previous final version of SAP**

Commercially Confidential Information (CCI)

**List of abbreviations**

Commercially Confidential Information	
AE	Adverse event
ANCOVA	Analysis of Covariance
Commercially Confidential Information	
AUC	Area Under the Curve
BMI	Body Mass Index
CSR	Clinical Study report
CTC	Common Toxicity Criteria
CTCAE	Common Terminology Criteria for Adverse Events
DMC	Data Monitoring Committee
ECG	Electrocardiogram
eGFR	Estimated glomerular filtration rate
FAS	Full Analysis Set
Commercially Confidential Information	
FXR	Farnesoid X receptor
HbA1c	Glycated haemoglobin
MedDRA	Medical Dictionary for Drug Regulatory Affairs
PK	Pharmacokinetics
PRO	Patient-reported Outcomes
RAP	Report and Analysis Process
SAP	Statistical Analysis Plan
SOC	System Organ Class
TFLs	Tables, Figures, Listings
VAS	Visual Analog Scale
WHO	World Health Organization

# 1 Introduction

The Statistical Analysis Plan (SAP) describes the implementation of the statistical analysis planned in the protocol.

## 1.1 Study design

[figure not shown]
This study is a non-confirmatory, multicenter, patient and investigator blinded, randomized, placebo-controlled, fixed-dose, proof-of-concept trial assessing LMB763 (nidufexor) vs. placebo in approximately 100 patients receiving standard of care (optimal tolerated doses of ARB or ACEI) for diabetic nephropathy due to type 2 diabetes. The study consists of a 30-day (Day -30 to Day-1) Screening period, followed by a 24-week Treatment Period (Days 1 through 168), at which point End of Study (EOS) assessments will occur on Day 169. All study visit assessments will occur pre-dose, starting on Day 1 of the therapeutic period. PK profiling (up to 6 hours post-dose) will be done on Day 1 and 14. Post Study Safety Contact will occur approximately 28 days after discontinuing study treatment (Day 197).

The study design scheme appears below. On visit days, study medication will be administered by site personnel. Each visit during the treatment and follow-up periods will have an allowable window of +/-5 days.

Safety assessments will include physical examinations, ECGs, vital signs, standard clinical laboratory evaluations (hematology, blood chemistry, urinalysis), adverse event and serious adverse event monitoring.

Commercially Confidential Information

Figure 1-1 LMB763X2202 study design

- Patients will be randomized in a 1:1 ratio to receive nidufexor CCI or placebo. Approximately 116 patients will be enrolled in the study and randomized. Approximately 100 patients are expected to complete the study.
- Study medication will be self-administered by patients CCI for 24 weeks. On visit days, study medication will be administered at the site.

## 1.2 Study objectives and endpoints

Objective(s)	Endpoint(s)
Primary objective(s)	Endpoint(s) for primary objective(s)

 
To compare the effect of nidufexor to placebo on albuminuria in patients with diabetic nephropathy already receiving treatment with ACEI or ARB
 
	
 
Urine albumin-creatinine ratio (UACR) at serial time points, as specified in the assessment schedule in the protocol
 
24-hour urinary albumin at baseline and end of study
 

 
To assess the safety and tolerability of nidufexor
 
	
 
Safety endpoints including: 
 
vital signs
 
physical examination
 
laboratory measurements
 
ECG parameters
 
adverse events
 
 
 

Secondary objective(s)	Endpoint(s) for secondary objective(s)

 
To determine the effect of nidufexor on renal filtration function
 
	
 
Estimated glomerular filtration rate (eGFR), as determined by the Chronic Kidney Disease Epidemiology Collaboration (CKD-EPI) equation (Levey and Stevens 2010)
 

 
To assess the pharmacokinetic properties of nidufexor on day 1 and at steady state in patients with type 2 diabetes and nephropathy
 
	
 
Cmax, Tmax and AUC0-6h.
 

 
To determine the effect of nidufexor on renal tubular function
 
	
 
Free water clearance
 

 
To determine the effect of nidufexor on anthropometric assessments
 
	
 
Assessments 
 
Weight
 
BMI
 
Waist-to-hip (WTH) ratio
 
 
 

 
To determine the effect of nidufexor on lipids
 
	
 
Fasting lipid profile, including lipoprotein (a) [Lp(a)]
 

---

Objective(s)	Endpoint(s)
---------------------	--------------------

---

Commercially Confidential Information

## **2 Statistical methods**

### **2.1 Data analysis general information**

Novartis will be performing primary/final analysis including interim analysis. SAS will be used to generate all the outputs. Baseline will be defined as the last measurement prior to the first administration of the study drug.

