## **4.2 Rationale for dose/regimen and duration of treatment**

Commercially Confidential Information

The CLMB763X2202 study population is expected to have comparable PK to the CLMBX2201 population.

Commercially Confidential Information

The duration of the study is based on (a) the high variability typical of urine albumin measurements, and (b) the high variability and slow rate of change in eGFR; the 24-week treatment period will allow more robust assessment of a potential anti-proteinuric effect (primary endpoint) and potential slowing of eGFR decline (secondary endpoint). Since both of these parameters demonstrate high intra- and inter-patient variability, repeated measures over 24 weeks will provide more robust data to detect potential treatment effects.

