## 5.1 Inclusion criteria

Patients eligible for inclusion in this study must meet **all** of the following criteria:

1. Written informed consent must be obtained before any assessment is performed
2. Male and female patients  $\geq 18$  years and  $\leq 75$  years (at the time of the screening visit).
3. Diagnosis of type 2 diabetes mellitus, with diagnosis made at least 6 months prior to screening, as determined by American Diabetes Association criteria  
[American Diabetes Association 2010](#)
4. Diabetic nephropathy as evidenced by Urine albumin-Cr ratio (UACR)  $\geq 300$  mg/g Cr at screening while receiving a dose of ACE-I or ARB that is the standard of care as judged by the PI or sub-I
  - Dose of ACE-I or ARB that is the standard of care as judged by the PI or sub-I *must also be stable, defined as <25% dose change that occurred at least 4 weeks prior to screening.*

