### **10.2.2 Renal safety monitoring**

Once a participant has been exposed to study treatment, the following two categories of abnormal renal laboratory alert values should be assessed during the study period:

Serum creatinine increase  $\geq 25\%$  compared to baseline during normal hydration status. Baseline serum creatinine is determined as the mean of two serum creatinine measurements (e.g. at screening and pretreatment).

- Albumin-creatinine ratio (UACR) increase  $\geq 2X$  baseline

Abnormal renal event findings must be confirmed within 24-48 hours after the first assessment.

Once a participant is exposed to study treatment, renal laboratory alerts or renal safety events should be monitored and followed up by the investigator or designated trial staff as summarized in [Table 16-3](#).

Every renal laboratory trigger or renal event as defined in [Table 16-3](#) should be followed up by the investigator or designated personnel as summarized in [Section 16.3](#).

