### **2.5.2.2 Efficacy and/or pharmacodynamic endpoints**

For all efficacy PD analyses, the PD set will be used.

A Mixed Model for Repeated Measures (MMRM) analysis will be performed for log-transformed ratio to baseline UACR measured at each visit. The model will include effects for log-transformed baseline, treatment, visit, treatment by visit interaction and visit by log-transformed baseline interaction. An unstructured variance-covariance matrix will be used to account for correlation among multiple measurements from the same patient and variance heterogeneity.

Similarly an Analysis of Covariance (ANCOVA) with treatment as the classification factor and log-transformed baseline as the covariate will be conducted for log-transformed ratio to baseline 24-hour urine albumin excretion.

Point estimates, the associated confidence intervals as well as the p-values for treatment difference at each visit will be provided within the MMRM/ANCOVA framework. The null hypothesis of no treatment difference in UACR or 24-hour urine albumin excretion will be tested at the one-sided 0.1 significance level. A treatment difference of at least 25% in favor of LMB763 will be considered clinically significant.

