### **2.5.3 Handling of missing values/multiple values/censoring/discontinuations.**

Missing data will not be imputed.

Assuming data is missing at random, a patient with a missing value at a visit will still contribute to the estimation of the treatment effect at that particular visit as the likelihood-based MMRM borrows information from non-missing values of this patient and other patients.

For central lab data collected at scheduled visits, the following sequential approach will be taken before data summary and analysis.

1. Take the average by subject, date and time for each parameter first.
- 2a. Derive baseline as the last available value prior to Day 1 dosing for each subject and parameter.
- 2b. Take the average by subject and visit for each parameter and then merge with the dataset containing baseline from 2a by subject and parameter.

The same approach as described above will be taken for vital sign and VAS data.

Local lab data will be included along with central lab data in the data listings and liver/renal event tables.

For ECG, 3 measurements on each visit are expected. The mean value will be used in the analyses even though the times are different.

For the analyses of liver abnormality and renal events, the most extreme value expressed as the multiple of the upper limit of normal (xULN) in a visit will be used for analyses.

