#### **2.5.4 Supportive analyses**

The raw value, ratio to baseline and log-transformed ratio to baseline of UACR will be plotted for each subject over time.

Absolute change from baseline in UACR and 24 hour UALB will also be analyzed using MMRM and ANCOVA, respectively.

The following supplementary analyses for UACR will be performed CCI separately.

1. Use value from Day 1 24 hour urine collection instead of last measurement prior to 1st dose as the baseline. Subjects without Day 1 value will be excluded from analysis.
2. Set assessments to missing if they were taken after dose reduction/interruption due to AEs and physician decision
3. Exclude subjects with baseline UACR < 300
4. Include all data from all randomized subjects and use the assigned treatment instead of the actual treatment received in the analysis (Intention to Treat, i.e., ITT)
5. Exclude week 24 measurements taken on day 134 or earlier from the ITT analysis
6. Exclude subjects with baseline UACR > 14000

The following supplementary analyses for 24 hour UALB will be performed separately.

1. Set assessments to missing if they were taken after dose reduction/interruption due to AEs and physician decision
2. Exclude subjects with baseline UACR < 300
3. ITT analysis
4. Exclude week 24 measurements taken on day 134 or earlier from the ITT analysis

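### The primary UACR model adjusts for one pre-dose reading only; adding the screening UACR as a second covariate would be a small, nearly free gain in precision

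*SAP*

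**What the plan says.** - **Baseline.** SAP 2.1: "Baseline will be defined as the last measurement prior to the first administration of the study drug". SAP 2.5.3, step 2a, repeats this for central laboratory data: "Derive baseline as the last available value prior to Day 1 dosing for each subject and parameter". Step 1 averages only values that share a date and time, so a screening reading is not averaged with a Day 1 reading.
- **Primary model.** SAP 2.5.2.2, for the log ratio to baseline UACR: "The model will include effects for log-transformed baseline, treatment, visit, treatment by visit interaction and visit by log-transformed baseline interaction". There is no other baseline term.
- **Screening value.** Protocol 5.1, criterion 4, requires a UACR of at least 300 "mg/g Cr at screening while receiving a dose of ACE-I or ARB that is the standard of care". Every eligible patient therefore has a screening UACR.
- **Supplementary analyses.** SAP 2.5.4, item 1 for UACR: "Use value from Day 1 24 hour urine collection instead of last measurement prior to" the first dose. It substitutes one single baseline for another. No visible item uses screening and Day 1 together.
- **Variability.** Protocol 4.2 justifies the study duration partly by "the high variability typical of urine albumin measurements", and says that variability is high both within and between patients.
- **Specimen.** Protocol Table 8-1, footnote 13, takes UACR from the 24-hour sample at visits that require one and from a spot sample otherwise.

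**The concern.** When a measurement varies a lot from day to day, one reading is an imperfect measure of a patient's underlying level, and adjusting for it removes less outcome variance than adjusting for two. The second reading is already in the database because eligibility depends on it. The Go rule in protocol 12.8.1 requires the point estimate to pass a fixed threshold, so the standard error of the treatment effect bears directly on the chance of a wrong decision. At stake is the width of the interval in a study of about 50 completers per arm. The validity of the comparison is not in question.

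**Working it through.** **Inputs from protocol 12.8.1:** 50 per arm, SD of the log ratio 0.6, true reduction 30%, Go threshold of a 25% estimated reduction, one-sided two-sample t-test. The one-sided level of 0.10 is in SAP 2.5.2.2. **Assumed, because the documents do not give them:** the correlations of log UACR between screening (s), Day 1 (d) and Week 24 (w).

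**1. The plan's own figure.** SE = 0.6 × √(2/50) = 0.12. The true effect is −ln 0.70 = 0.357 and the Go threshold is −ln 0.75 = 0.288. Significance needs only about 1.29 × 0.12 = 0.155, so the 25% criterion binds. P(Go) = Φ((0.3567 − 0.2877)/0.12) = Φ(0.575) = 71.7%. The stated 72% reproduces. It comes from an unadjusted test, so it does not depend on any baseline covariate.

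**2. Saving from a second covariate.** The proportional fall in residual variance is the squared partial correlation:

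(r_sw − r_sd·r_dw)² / [(1 − r_sd²)(1 − r_dw²)]

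If all three correlations equal r, this becomes r²/(1 + r)²: 8.2% at r = 0.4 and 18.9% at r = 0.77.

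**3. Selection at screening.** Simulation kept only patients with screening UACR ≥ 300 mg/g, assuming a log SD of 1 and an unselected median of 300 to 1000 mg/g. The saving falls to 3.5–6.1% at r = 0.4 and 12.1–16.5% at r = 0.77.

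**4. Screening a weaker predictor of Week 24 than Day 1, without selection.** Averaging s and d leaves residual variance 1 − [(r_dw + r_sw)/2]² / [(1 + r_sd)/2], compared with 1 − r_dw² for Day 1 alone.

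| r_sd | r_sw | r_dw | Second covariate saves | Averaging saves |
|---|---|---|---|---|
| 0.80 | 0.55 | 0.60 | 2.1% | 1.2% |
| 0.80 | 0.60 | 0.70 | 0.9% | −4.0% |
| 0.90 | 0.72 | 0.80 | 0.0% | −8.9% |

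Second row, covariate: (0.60 − 0.56)² / (0.36 × 0.51) = 0.0016/0.1836 = 0.9%. Second row, averaging: 1 − 0.4225/0.9 = 0.531 against 0.51, a loss of 4%. The third row is the limiting case r_sw = r_sd·r_dw, where screening adds nothing once Day 1 is known.

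**5. Effect on Go**, taking 0.6 as the residual SD:
- 1% saving: SE 0.1194, P(Go) 71.8%.
- 17% saving: SE 0.12 × √0.83 = 0.1093, P(Go) = Φ(0.631) = 73.6%.

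If 0.6 is instead the SD of the unadjusted log ratio, the adjusted residual SD is 0.6 × √((1 + r)/2), which is 0.564 at r = 0.77. P(Go) then goes from 73.0% to 74.8% with a 16.5% saving.

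**6. Cost in degrees of freedom.** With 100 completers and one extra coefficient at Week 24, the expected variance of the effect is multiplied by (1 + 2/95)/(1 + 1/96) = 1.0105, about 1%. At the bottom of the range the gain and the cost cancel.

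**The case against.** The last pre-dose value is a conventional baseline and has real advantages. It is nearest to dosing. It is not itself the value on which patients were selected at 300 mg/g, so it is less exposed to regression to the mean. Screening can be up to 30 days earlier. Exclusion criterion 18 admits patients who switch from prohibited drugs at least 5 days before the first dose, so screening UACR may precede a change in background therapy. Day 1 UACR may come from the 24-hour sample, as at Week 24, while screening may be a spot sample. All of this stands. It tells against averaging, or against putting screening in the denominator. It does not tell against a second covariate, whose weight is estimated from the data.

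A reader might infer more than the documents support:
- **That the plan gives away 8–19% of residual variance for nothing.** The two ends are the equal-correlation results at r = 0.4 and 0.77. The documents give no correlations, and the saving shrinks under selection or unequal prediction.
- **That the protocol's creatinine rule sets a precedent.** Protocol 10.2.2 says "Baseline serum creatinine is determined as the mean of two serum creatinine measurements", but that governs a safety alert. The UACR alert in the same section specifies no averaging.
- **That supplementary analysis 1 concedes the point.** It changes which single value serves as baseline and does not address the noise of a single reading.

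The UACR row of Table 8-1, protocol 12.4.4 and part of SAP 2.5.4 are not in the public text. The screening specimen type and the full list of sensitivity analyses therefore cannot be confirmed.

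**Conclusion.** The point holds as an efficiency suggestion. The primary model uses one pre-dose reading where two are available by design, and a second covariate can be added without biasing the randomised comparison. The saving in residual variance is about 1–17%, under assumed between-visit correlations and after allowing for selection at screening or unequal correlations. It reaches zero in the limiting case where screening carries no information beyond Day 1. The probability of Go at a true 30% reduction rises by at most about 1–2 points. A reading that the planned baseline is an error, or that it biases the treatment effect, is not supported: the comparison is randomised, and the ANCOVA-type adjustment already improves on the unadjusted test used for planning.

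**What to change.** In SAP 2.5.2.2, before unblinding:
- Keep the last pre-dose UACR as the denominator of the ratio and as the baseline covariate.
- Add log screening UACR and its visit interaction as a second covariate in the primary UACR MMRM. Where screening is itself the last pre-dose value, both covariates take that value.
- Keep the current single-baseline model as a supplementary analysis.
- Do not average screening and Day 1. The readings may differ in specimen, timing, background therapy and selection.
- Record the addition in SAP section 3, since protocol 12.4.2.2 lists the model terms without it.

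The cost is a few lines of SAP text and one coefficient per analysed visit. No new data or procedures are needed.
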